1. OBJECTIVES

1.1 Study Design

This is a single-arm, two-stage Phase 2 study assessing the efficacy of AZD1775, a Wee1 tyrosine kinase inhibitor, given in combination with cisplatin chemotherapy. The population to be studied will consist of approximately 35 patients with metastatic triple-negative breast cancer who have received 0 to 1 line of chemotherapy in the metastatic setting. All patients must have measurable disease at baseline and have archival tissue available. Treatment will consist of one cycle of cisplatin monotherapy (cisplatin 75 mg/m2 IV x1) followed by combination therapy of AZD1775 plus cisplatin starting 21 days later. AZD1775 will be administered as twice daily oral dosing (AZD1775 200 mg po bid) x 5 doses over 2.5 days, in combination with cisplatin 75 mg/m2 IV every 21 days. At least 10 patients will undergo a research biopsy within 5-48 hours after cisplatin monotherapy and then again within 5-8 hours after the last dose of AZD1775 in cycle 2 of cisplatin +AZD1775. Patients will undergo restaging scans every 6 weeks, those with complete responses, partial responses, and stable disease, will continue to receive study treatment. Patients with progressive disease will be taken off study.

1.2 Primary Objectives

The primary objective of the study is:

1. To evaluate the activity of AZD1775 in combination with cisplatin, as defined by objective response rate (ORR) in patients with triple-negative metastatic breast cancer

1.3 Secondary Objectives

The secondary objectives of the study are:

- 1) To evaluate Progression Free Survival (PFS).
- 2) To evaluate change in pCDC2 after therapy with AZD1775 in paired biopsies
- 3) Evaluate incidence of p53 mutations in tumor tissue and correlate mutational status with response
- 4) To evaluate change in markers for DNA damage (gamma-H2AX, phospho-Histone 3, and caspase 3) after exposure to cisplatin + AZD1775 compared to cisplatin therapy alone in paired biopsy samples
- 5) To evaluate the incidence BRCA1 and BRCA2 mutations, and correlate mutational status with response

- 6) To explore other possible gene mutations that may correlate with response.
- 7) To correlate next generation sequencing of tumors with participant outcomes (ORR and PFS) in DFCI participants only.

2. BACKGROUND

2.1 Study Disease(s)

Breast cancer is the most commonly diagnosed cancer and the second leading cause of cancer death in American women. Despite recent advances in breast cancer treatment, metastatic disease remains incurable. One possible limitation of our therapies has been an inability to select subsets of patients most likely to benefit from specific therapies. With the development of gene expression array technology, the heterogeneity of breast cancer has become clearer and the identification of novel cancer subtypes has reinvigorated the search for more specific and effective therapies. Hierarchical clustering of genomic expression data from breast cancer specimens have demonstrated several distinct tumor subgroups with unique expression profiles, including a HER2-positive subgroup, an estrogen-receptor (ER)positive group, and a "basal-like" group.¹ Hormonal therapies are only effective for ER or PR positive breast cancer, and the monoclonal antibody trastuzumab is effective only for tumors that have amplified HER2 genes.

The basal-like tumors have a poor prognosis relative to other subtypes¹, even with the best available chemotherapy. Approximately 15% of women are diagnosed with this form of breast cancer, with a disproportionate distribution in younger women or BRCA1 mutation carriers. Little progress has been made in identifying specific molecular pathways associated with these refractory cancers that may be effectively targeted for therapeutic purposes. Thus, no proven, specific therapy exists for this tumor subtype. A common feature of tumors in the basal-like subgroup is the lack of expression of ER, PgR, and HER2 (hence the term 'triple-negative' breast cancer) as well as the expression of the Epidermal Growth Factor Receptor (EGFR) and certain cytokeratins (cytokeratin 5/6) that indicate a basal differentiation for these breast tumors². The gene expression signature of the basal-like tumors shows high levels of expression of proliferation-associated genes and genes that are normally expressed in myoepithelial or basal cells of normal breast tissue, such as the basal keratins and smooth muscle actin. There are similarities between this subgroup and tumors with germline BRCA1 mutations, which also typically lack ER and PR receptors, are histologically high grade, and are reported to be positive for basal-like keratins^{3,4}.

2.2 AZD1775

Cytotoxic agents remain a key component of cancer therapy. Tumor cells rely on cell cycle checkpoints for repair of DNA damage induced by cytotoxic agents. Cytotoxic agents that induce DNA damage activate cell cycle checkpoints in proliferating cells. These checkpoints cause transient arrest at the G1-, S-, and G2-phase of cycling cells, allowing time to repair the DNA or initiate apoptosis if the DNA damage is too extensive. Human tumor cells are most sensitive to

chemotherapy during the phase of DNA replication (S-Phase) which is variable in length and lasts up to ~60 hrs in human tumors in-situ. While DNA checkpoints can protect normal cells from DNA damage, they also reduce the effectiveness of chemotherapy on tumor cells by allowing tumor cells to repair DNA damage induced by chemotherapy. Thus, selective inhibition of checkpoints in tumor cells is predicted to enhance the efficacy of DNA-damaging agents since mutations will not be repaired^{5–7}.

Wee1 is a tyrosine kinase that selectively phosphorylates the Tyr15 residue of cyclin-dependent kinase 1 (also known as CDC2) and inactivates its activity. Report AZD1775 is a highly selective, small-molecule, inhibitor of Wee1 kinase activity. The protein p53 regulates the G1 checkpoint, while the Wee 1 tyrosine kinase regulates the G2 checkpoint by selectively phosphorylating CDC2. Phosphorylation of CDC2 inhibits its kinase activity, which abrogates G2 cell cycle arrest after DNA damage. Therefore, p53 deficient tumor cells lacking the G1 checkpoint are dependent on the G2 checkpoint for survival following DNA damage. G2 checkpoint abrogation is a therapeutic strategy designed to prevent cell cycle arrest in response to DNA damage, resulting in impaired DNA repair and increased tumor cell death^{5,6}. Because wild type p53 cells retain both the G1 checkpoint and back-up p53-dependent pathways at the G2 checkpoint, G2 checkpoint abrogation in combination with DNA damage in p53 deficient cells is expected to selectively enhance cell death¹².

2.3 Cisplatin

Cisplatin and Breast Cancer

Platinum was studied in breast cancer in the 1970s and was shown to be active when given early in the course of the disease, but it was not adopted, perhaps because of the superior therapeutic index of other drugs then under development (the taxanes). The drug was initially tested in patients with advanced breast cancer, both as a single agent and in combination with other drugs. Small studies demonstrated objective response rates ranging from 42% to 54% with the use of cisplatin as a single agent, but response rates were lower in women who had received prior chemotherapy for metastatic disease^{13–15}. When cisplatin was given after other chemotherapy, the response rate fell to 0-9%^{16–20}.

Notably, these studies used cisplatin in patients regardless of ER, PgR, and HER2 status. Several combination regimens were also explored, particularly cisplatin combined with taxanes, but there seemed little reason to continue these combinations when the taxanes were found to be so active and relatively nontoxic²¹. There was also interest in the evaluation of combined treatment with docetaxel and platinum. In several studies in unselected cases of metastatic disease, the overall response rate with combination regimen was around 50%, even with prior adjuvant anthracycline therapy²¹.

There has recently been renewed interest in cisplatin for the treatment of breast cancer, in part because of improved strategies for managing its side effects, particularly nausea. A 2004 phase 2 study of preoperative paclitaxel and cisplatin demonstrated a 28% complete response rate and a 63% partial response rate in patients enrolled without regard to ER, PgR, and HER2 status²². These rates are comparable to those for other active regimens.

Published data on response rates with cisplatin used as a single agent in women with metastatic breast cancer unselected for breast cancer subtype are summarized in Table 2.3.1. Recent data from TBCRC009 demonstrated that platinum therapy (carboplatin or cisplatin) resulted in a response rate of 25.6% in the first or second line setting for metastatic triple-negative breast cancer, suggesting that these agents are active. The Triple Negative Breast Cancer Trial (TNT) study directly compared single-agent platinum chemotherapy with taxane therapy in the first line treatment of metastatic triple-negative breast cancer. Patients were randomized to carboplatin or docetaxel, and the objective response rate in the carboplatin arm was 31.4% compared to 35.6% in the docetaxel arm, which was not statistically different (p=0.44). However, among the 43 patients with a BRCA mutation, the objective response rate was 68% with carboplatin and 33% with docetaxel, which was statistically significant (p=0.03).

Table 2.3.1 Single-Agent Cisplatin in Metastatic Breast Cancer

Table 2.3.1 Single-Agent Cispiatin in Metastatic Breast Cancer				
Cisplatin Dose	Response Rate	Reference No.		
No Prior chemotherapy				
30mg/m ² /d x 4 d every 3 wk	13/35	5		
30mg/m ² /d x 4 d every 3 wk	5/12	6		
30mg/m ² /d x 4 d every 3 wk	9/19	7		
Total	33/66(60%)			
Prior chemotherapy				
35mg/m ² /d x 5 d every 4 wk	2/5	8		
15mg/m ² /d x 5 d every 4 wk 100-120mg/m ² every 4 wk	0/15 2/13	10		
60mg/m ² every 3-4 wk 120mg/m ² every 3-4 wk	0/18 4/19	9		
100mg/m ² every 3-4 wk	2/17	11		
20mg/m ² /d x 5 d every 4 wk 100mg/m ² every 3-4 wk	0/14 0/12	12		
Total	10/113(9%)			

Cisplatin and Basal-Like Breast Cancer

Basal-like breast cancers share many molecular features with BRCA1-associated breast cancer, a subset which have recently been shown to be more sensitive to cisplatin. Recent preclinical work has identified that platinum agents may be particularly active in a subset of triple-negative

breast cancer.²³ Cytotoxic agents, such as cisplatin, induce DNA damage that activates cell cycle checkpoints. These checkpoints results in transient arrest at the G1-, S-, and G2- phases of cycling cells, allowing time to repair the DNA damage or to initiate apoptosis, if the DNA damage is too extensive. While DNA checkpoints can protect normal cells from DNA damage, they also reduce the effectiveness of chemotherapy on tumor cells by allowing tumor cells to repair DNA damage induced by chemotherapy.

2.4 Rationale

While only about 20% of breast cancer is p53 deficient, approximately 60-80% of triple-negative breast cancers appear to have p53 pathway deficiency²⁴, suggesting that AZD1775 would be expected to have more selective chemosensitization effects for this tumor subtype. In addition, in both in vitro and in vivo xenograft tumor models, AZD1775 in combination with gemcitabine or platinum chemotherapy caused significantly greater efficacy than gemcitabine or platinum alone¹². Additionally, we have treated 5 patients on protocol 001-07 (DF/HCC protocol 08-030) with metastatic triple-negative breast cancer with AZD1775+ cisplatin. Of these 5 heavily pretreated patients, 1 had a PR and 3 had SD as their best response. ²⁵ Additionally, in a randomized phase 2 study in women with TP-53 mutant ovarian cancer, AZD1775 plus paclitaxel and carboplatin was associated with a significant improvement in progression-free survival compared with chemotherapy alone, suggesting activity for this agent when given in combination with platinum-based chemotherapy (REF: Oza et al ASCO 2015).

We propose a trial to look at cisplatin in combination with AZD1775 for metastatic triplenegative breast cancer.

2.5 Correlative Studies Background

We plan to demonstrate target engagement in tumor tissue by analysis of changes in pCDC2. Changes in pCDC2 have been seen in skin biopsies of patients receiving AZD1775, ²⁶ and recently has also been demonstrated in 3 of 5 paired biopsies in patients receiving AZD1775 as monotherapy in a phase 1 trial (REF: Do et al., JCO 2015).

Patients will receive cisplatin monotherapy for 1 cycle upfront, followed by cisplatin + AZD1775 for subsequent cycles of therapy. Any patient with tumor that is accessible to biopsy will undergo research biopsies after one dose of cisplatin, and after the combination therapy. We anticipate that pCDC2 will be present after cisplatin monotherapy. After the combination, a reduction in pCDC2 relative to CDC2 is expected. This should be accompanied by evidence of checkpoint bypass and entrance of tumor cells into mitosis, which will be assessed by an increase in phospho-Histone 3 after combination treatment compared to cisplatin monotherapy. Checkpoint bypass will result in greater DNA damage, which should cause an increase in gamma-H2AX after combination treatment.²⁷ Finally, entrance of cells into mitosis without adequate DNA repair is frequently lethal and should result in increased apoptosis, which can be assessed with an increase in cleaved caspase 3 after combination treatment.²⁸

Historically, it has been challenging to study the molecular evolution of tumors over time and through progression on serial treatment regimens. However, emerging technology now permits whole exome sequencing from cell-free DNA (cfDNA) isolated from fresh blood. We aim to examine the utility of this approach for detecting molecular changes in individual patients' tumor cell populations over time by performing serial cfDNA.

We will access DNA sequencing data (where possible) on tumors from all DFCI participants who previously had tumor sequencing performed under the Dana-Farber Cancer Institute's "Profile" targeted sequencing panel. MGH participants and any 16-264 participants who did not previously participate on or have sequencing performed under "Profile" will be excluded from any analysis. We will use these data to investigate candidate genomic correlates of response, including tumor mutation burden and alterations in genes involved in homologous recombination, DNA damage response, and cell cycle G1/S checkpoint signaling. Mutations in G1/S checkpoint genes, such as *TP53*, *MYC*, and *CCNE1*, may enhance reliance on the Wee1-mediated G2/M checkpoint for accurate DNA repair and therefore make these tumors more susceptible to the combination of AZD1775 and cisplatin. Altogether, these existing DNA sequencing data may reveal preliminary response biomarkers to guide future DNA and RNA sequencing studies.

3. PARTICIPANT SELECTION

3.1 Inclusion Criteria

- 3.1.1 Participants must have histologically or cytologically confirmed invasive breast cancer, with either locally advanced or metastatic disease. Patients without pathologic or cytologic confirmation of metastatic disease should have unequivocal evidence of metastasis from physical examination or radiologic evaluation.
- 3.1.2 Either the primary invasive tumor and/or the metastasis must be triple-negative, defined as:
 - hormone-receptor poor, ER- and PR-negative, or staining present in <1% by immunohistochemistry (IHC)
 - HER2-negative: 0 or 1+ by IHC, or FISH<2.0

- 3.1.3 Participants must have at least one lesion that is not within a previously radiated field that is measurable on computerized tomography (CT) or magnetic resonance imaging (MRI) scan per RECIST version 1.1. Bone lesions are not considered measurable by definition. See Section 11 for the evaluation of measurable disease.
- 3.1.4 Prior chemotherapy: Patients may have received 0-1 prior chemotherapeutic regimen for metastatic breast cancer and must have been off treatment with chemotherapy for at least 21 days before enrollment in the study. The number of patients with 0 prior chemotherapeutic regimen will be limited to a maximum of n = 20.
- 3.1.5 Prior biologic therapy: Patients must have discontinued all biologic therapy at least 21 days before participation.
- 3.1.6 Prior radiation therapy: Patients may have received prior radiation therapy in either the metastatic or early-stage setting. Radiation therapy must be completed at least 14 days prior to study participation and patients should have recovered from adverse effects of radiation to grade ≤1.
- 3.1.7 Age ≥ 18
- 3.1.8 ECOG performance status ≤1
- 3.1.9 Participants must have normal organ and marrow function as defined below:
 - Absolute neutrophil count ≥1500/mm³
 - Platelets $\geq 100.000/\text{mm}^3$
 - Hemoglobin ≥9 g/dL
 - Total Bilirubin ≤1.5 mg/dL
 - Serum creatinine ≤1.5 mg/dL OR measured creatinine clearance (CrCl) ≥45 mL/min as calculated by the Cockcroft-Gault method OR 24-hour measured urine CrCl ≥45mL/min
 - Alanine aminotransferase (ALT) and aspartate aminotransferase (AST) ≤2.5 times the upper limit of normal. For patients with documented liver metastases, AST/ALT ≤ 5.0 times the upper limit of normal.

- 3.1.10 Patients on bisphosphonates may continue receiving bisphosphonate therapy during study treatment.
- 3.1.11 Availability of a tissue block from initial breast cancer diagnosis and/or metastatic recurrence. If a tissue block is not available, 10-20 unstained slides may be provided as an alternative. If unstained slides will be provided, they should not be sent until specifically requested by the DFCI study coordinator. If archival tumor tissue is not available, a fresh biopsy may be performed.
- 3.1.12 All patients with biopsy-accessible disease must be willing to undergo paired research biopsies. These biopsies will occur 5-48 hours after the C1D1 cisplatin dose (ie. C1D2or C1D3) and 5-8hrs (+/- 24hrs) after the last dose of AZD1775 on C2D3. The exact timing of the biopsy relative to receipt of study treatment should be accurately recorded.
 - Biopsies may be done with local anesthesia or intravenous conscious sedation, according to standard institutional guidelines.
 - Research biopsies requiring general anesthesia are not allowed on this protocol unless a biopsy is being obtained simultaneously for clinical reasons, in the judgment of the patients' treating physician.
 - Patients who undergo an attempted on-treatment research biopsy and in whom inadequate tissue is obtained are still eligible to continue protocol therapy. They will not be required to undergo a repeat biopsy attempt.
 - If dosing is delayed placing the biopsy outside of the allowable window, the biopsy should be rescheduled to be within the window. If not feasible, the biopsy should be obtained as close to within the window as possible.
 - Fine needle aspirates (FNA) is not allowed
- 3.1.13 Female subjects of childbearing potential must have a negative serum pregnancy test at screening.
- 3.1.14 The effects of AZD1775 on the developing human fetus are unknown. Women of child-bearing potential and men must agree to use enhanced methods of contraception. All women are considered to be of childbearing potential unless they fulfill one of the following criteria at screening:
 - Post-menopausal defined as age ≥50 and amenorrheic for at least 12 months OR
 - Women age <50 if they have been amenorrheic for at least 12 months and have a serum follicle-stimulating hormone (FSH) and luteinizing hormone (LH) level in the postmenopausal range (per institutional standards).
 - If women have documentation of irreversible surgical sterilisation by hysterectomy, bilateral oophorectomy, or bilateral salpingectomy, or bilateral tubal ligation, they are considered post-menopausal.

- 3.1.15 Appropriate contraception should be used from the time of screening, throughout the duration of study participation, and for four months after the last dose of AZD1775. Acceptable methods of contraception include abstinence, tubal ligation, intra-uterine devices, and vasectomised partner. All methods of contraception (with the exception of total abstinence) should be used in combination with the use of a condom by the male sexual partner for intercourse. Should a woman become pregnant or suspect she is pregnant while she or her partner is participating in this study, the participants treating physician should be informed immediately. Additionally, male patients should refrain from donating sperm from the start of dosing until 6 months after discontinuing AZD1775. If male patients wish to father children they should be advised to arrange for freezing of sperm samples prior to the start of study treatment.
- 3.1.16 Participant must be able to swallow pills.
- 3.1.17 Participant may not have a percutaneous endoscopic gastrostomy (PEG) tube or be receiving total parenteral nutrition (TPN).
- 3.1.18 Ability to understand and the willingness to sign a written informed consent document.

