5.3 Agent Administration

5.3.1 *AZD1775*

Dose: 200mg po bid x 5 doses

AZD1775 will be administered bid for two and a half days starting concomitantly with the administration of cisplatin with cycle 2. The patient will take the first dose of AZD1775 in clinic on cycle 2 day 1, and subsequent doses that cycle can be taken at home. On cycle 2 day 1 and subsequent day 1 visits, AZD1775 and cisplatin may be administered concurrently. There is no preferential order of administration. The subsequent 4 additional doses of AZD1775 are to be taken in approximately 12 hour increments. Participants should take AZD1775on an empty stomach and should not have food 2 hours before or 2 hours after the dose. If the participant misses a dose by < 6 hours from scheduled dose, the dose should not be made up. If the participant vomits after the administration of AZD1775, the dose should not be readministered. AZD1775 should not be crushed, chewed or dissolved in water.

Premedication:

All patients must receive a 5-HT3 antagonist prior to each dose of AZD1775. In addition, dexamethasone 4 mg PO will be given with each AZD1775 dose as a minimum on the first day of dosing AZD1775 of every 3-5 days dosing period, unless contraindicated or not well-tolerated. Dexamethasone or the 5-HT3 antagonist may be given by IV.

5.3.2 *Cisplatin*

Administration

- **Dose**: Cisplatin 75mg/m² IVB q3 weeks (every 21 days, plus minus 3 days for scheduling issues). Cisplatin may be administered according to institutional guidelines at participating sites. The preferred guidelines are as described below.
- Infusion time: 60 minutes.
- **Pretreatment hydration**: Hydration may be achieved by IV infusion of 1 liter of sodium chloride 0.9% (±potassium 20 meq) over 1-2 hours prior to Cisplatin infusion.
- **Pretreatment Magnesium Supplementation**: As needed, give prior to Cisplatin, Magnesium Sulfate 2 GM IV×1.
- Treatment: Ensure there is adequate urine output averaging at least 100cc/hr prior to Cisplatin infusion. As needed, give 12.5mg IVB of MANNITOL 25% 30 minutes prior to Cisplatin infusion. Mix Cisplatin in 100-500ml sodium chloride 0.9% and infuse IVB over 60 minutes. Post-treatment hydration: Participants should receive 1 liter of sodium chloride 0.9% (±potassium 20 meq) IV over 1-2 hours after Cisplatin administration.
- **Post-treatment hydration:** Participants should receive 1 liter of sodium chloride 0.9% (±potassium 20 meg) IV over 1-2 hours after Cisplatin administration.

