9. BIOMARKER, CORRELATIVE, AND SPECIAL STUDIES

9.1 Biomarker Studies

All biomarker analyses completed on blood and tissue samples for correlative data will be exploratory.

Weel kinase is a regulator of the G2/M checkpoint. As Weel phosphorylates CDC2 in response to genotoxic insults, inhibition of CDC2 phosphorylation by a Weel inhibitor is considered a direct measure of target engagement. Under normal conditions, pCDC2 levels in tissue is quite low. Changes in pCDC2 is contingent upon pCDC2 induction by DNA damage. Patients will therefore undergo tumor biopsies after one dose of cisplatin, and then again after a dose of cisplatin + AZD1775.

Formalin-fixed, paraffin-embedded (FFPE) biopsy specimens will be subjected to immunohistochemical analyses using standard procedures for: (1) Total CDC2; (2) phospho-CDC2; (3) gamma-H2AX; (4) phospho-Histone 3; and (5) cleaved caspase 3.

For total CDC2, phospho-CDC2, phospho-Histone 3 and cleaved caspase 3, immunohistochemical sections will be scored manually and the % positive cells will be annotated; a minimum of 200 cells will be counted. Additionally, stained slides will be scanned using an Aperio ScanScope XT workstation (Aperio Technology, Inc., Vista, CA). Images will be visualized and digitally annotated (as regions of interest, ROIs) using ImageScope software (version 10.0.35.1800, Aperio Technology). The ROIs will then be analyzed using a standard

analysis algorithm to quantitate the proportion of area that is positive for staining (color deconvolution v9.0, Aperio Technology). The expected result after cisplatin/AZD1775 compared to cisplatin alone is preserved total CDC2 staining, reduced phospho-CDC2 staining, increased phospho-Histone 3 staining and increased cleaved caspase 3 staining. In phase 1 studies, in which skin biopsies were analyzed, a decrease of phospho-CDC2 in the presence of AZD1775 of at least 50% was considered to represent evidence of target engagement. In a study of AZD1775 monotherapy, increases in gamma-H2AX were seen in 3 of 5 paired biopsies. We will analyze changes in phospho-CDC2 (using this parameter alone); additionally, the change in ratio of phospho-CDC/total CDC2 will also be assessed when biopsies post-cisplatin/AZD1775 and post-cisplatin alone are compared.

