Immunohistochemistry for gamma-H2AX [pSer139] will be scored manually with a determination of the percentage of cells containing at least 5 nuclear foci.^{3,4} It is expected that the percentage of foci-positive cells will be greater after cisplatin/AZD1775 compared to cisplatin alone. This work will be performed in collaboration with [name], who was the DF/HCC PI on the Phase I trial of chemotherapy combinations with AZD1775, and [name] [name], who is internationally recognized expertise in the assessment of DNA damage pathways, and with [name], a pathologist in the DF/HCC Pathology Core at Brigham and Women's Hospital, who has extensive experience with analysis of these markers.

The study will obtain paired tumor biopsies for all patients enrolled with accessible disease (after cisplatin monotherapy and after cisplatin + AZD1775 combination therapy). The analysis will treat the quantification of pCDC2, gamma-H2AX, phospho-Histone 3, and cleaved caspase 3 as continuous variables. To evaluate change in these marker levels after the addition of AZD1775, descriptive statistics for the change will be generated. Paired t-tests or Wilcoxon signed rank test, whichever is appropriate considering the data distribution, will also be used to describe change in marker levels.

Biopsy samples will also be subjected to whole exome sequencing (WES) to capture (1) BRCA reversion mutations as well as the mutation status of most genes involved with double strand break repair (2) evidence of telometric allelic imbalance, a predictor of cytotoxic therapy response⁵, (3) overall mutational signature, and (4) cell cycle genes related to G1/S checkpoint, that may enhance reliance on Wee1-mediated G2/M checkpoint for proper DNA repair.⁶

The prevalence of BRCA 1 and BRCA2 mutations is approximately 10-15% among patients with triple-negative breast cancer.³⁷ Breast cancers with BRCA deficiency may be more susceptible to increases in DNA damage provoked by combination therapy with cisplatin and AZD1775. For patients in whom BRCA status is unknown, anonymized blood samples will be undergo testing for BRCA 1 and 2. We will determine whether there is an association between germline BRCA deficiency and response to therapy.

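### The two biopsies of a pair are set at different nominal times after cisplatin, need not match and are not adjusted for, so the paired marker change cannot separate AZD1775 from the cisplatin time course

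*Combined protocol and SAP*

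**What the plan says.** - **First biopsy.** Section 3.1.12: "These biopsies will occur 5-48 hours after the C1D1 cisplatin dose". That section places it on day 2 or day 3 of cycle 1. Table 9-1, Section 9.2.3.2, footnote i of the study calendar and Appendix C give the same hours but label the visit day 1.
- **Second biopsy.** Section 3.1.12: "5-8hrs (+/- 24hrs) after the last dose of AZD1775 on C2D3". Table 9-1, Section 9.2.3.2, the calendar footnote and Appendix C also carry the 24 h tolerance. Section 1.1 does not: "again within 5-8 hours after the last dose of AZD1775 in cycle 2 of cisplatin +AZD1775".
- **Dosing in cycle 2.** Section 5.3.1: "AZD1775 will be administered bid for two and a half days starting concomitantly with the administration of cisplatin with cycle 2" and "The subsequent 4 additional doses of AZD1775 are to be taken in approximately 12 hour increments". The order of the two drugs on day 1 is left open.
- **Why there is a cisplatin-only biopsy.** Secondary objective 4 compares the combination with cisplatin alone within patients, and objective 2 is the change in pCDC2. Section 9.1 says that resting pCDC2 is low and adds: "Changes in pCDC2 is contingent upon pCDC2 induction by DNA damage".
- **Analysis.** Section 9.1: "To evaluate change in these marker levels after the addition of AZD1775, descriptive statistics for the change will be generated". A paired t-test or Wilcoxon signed rank test is added. Neither Section 9.1 nor Section 13.3 uses the time of biopsy. Section 3.1.12 does require the exact timing to be recorded, and Section 9.1 labels all biomarker analyses exploratory.

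**The concern.** The cycle 1 biopsy is there to show what cisplatin does without AZD1775. It serves that purpose only if the tumour is sampled at a comparable time after cisplatin in both cycles. On the protocol's own account the markers respond to DNA damage: pCDC2 has to be induced by it, and Section 2.2 describes checkpoint arrest as transient, ending in repair or apoptosis. A tumour sampled on day 1 or 2 in one cycle and late on day 3 in the next could show a different pCDC2, gamma-H2AX, phospho-Histone 3 or caspase 3 level with no contribution from AZD1775.

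At stake is the interpretation of secondary objectives 2 and 4. A fall in pCDC2 would be read as target engagement, and a rise in damage or apoptosis markers as enhancement of cisplatin. Drift in the opposite direction could mask a real effect.

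**Working it through.** **1. The plan's own power figures.** Section 13.3 assumes 18 pairs, a mean difference of 0.5, SDs of the paired difference of 0.5, 0.75 and 1, and one-sided alpha 0.05. Exact paired t: df = 17, critical value 1.740, noncentrality = (difference/SD) x sqrt(18).

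| SD | Noncentrality | Power | Plan |
|---|---|---|---|
| 0.5 | 4.243 | 99.2% | 99% |
| 0.75 | 2.828 | 85.7% | 86% |
| 1 | 2.121 | 65.2% | 65% |

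The figures reproduce. They treat the whole difference as the AZD1775 effect.

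**2. Hours after same-cycle cisplatin.** The first AZD1775 dose is at about 0 h and four more follow at about 12 h, so the last is at 4 x 12 = 48 h. The nominal second biopsy is at 48 + 5 = 53 h to 48 + 8 = 56 h. With the tolerance it runs from 53 - 24 = 29 h to 56 + 24 = 80 h.

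| Reading of the second window | Second biopsy | Overlap with 5-48 h | Second minus first |
|---|---|---|---|
| Nominal (as in Section 1.1) | 53-56 h | none | 5 to 51 h |
| With +/- 24 h | 29-80 h | 29-48 h | -19 to 75 h |
| With +/- 24 h, but after the last dose | 48-80 h | 48 h only | 0 to 75 h |

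The nominal midpoints are 26.5 h and 54.5 h, 28 h apart. The gap is smaller if the first biopsy is never on day 1.

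The dose spacing is approximate and the drug order is free, so the nominal window can move. With assumed 11 h spacing and AZD1775 taken 4 h before cisplatin, it is -4 + 44 + 5 = 45 h to -4 + 44 + 8 = 48 h. This shifts the window; it does not match the pair.

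**3. What the paired mean estimates.** Mean change = AZD1775 effect + (marker level at the second time - marker level at the first time, both after cisplatin alone). The design has no observation that isolates the bracketed term, and the analysis does not model it.

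**4. Size, under an assumed drift.** Let d be the drift in SDs of the paired difference, with no AZD1775 effect. P(reject) comes from the noncentral t with noncentrality d x sqrt(18).

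| d, in the tested direction | Noncentrality | P(reject) at nominal 5% |
|---|---|---|
| 0 | 0 | 5.0% |
| 0.2 | 0.849 | 20.3% |
| 0.3 | 1.273 | 33.6% |
| 0.5 | 2.121 | 65.2% |

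For drift against the tested direction, take the plan's base case (difference 0.5, SD 0.5, standardised effect 1). A drift of 0.2 SD leaves 1 - 0.2 = 0.8 and power of 94.6%; a drift of 0.5 SD leaves 0.5 and power of 65.2%, down from 99.2%.

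**The case against.** The strongest reply is that the text allows more than the nominal times suggest. A reader might infer that the two biopsies can never fall at the same time after cisplatin, or that the gap is always 5 to 51 h. The documents do not support that: with the 24 h tolerance a pair can coincide anywhere from 29 to 48 h. This stands, with a limit. Any time before 48 h precedes the fifth AZD1775 dose, which conflicts with a biopsy defined as following the last dose. The tolerance also widens the possible gap to 75 h, and it permits matching without requiring it.

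A reader might also take 20-65% as the error rate of this trial. It is not. The documents contain no marker time course after cisplatin, so both size and direction of drift are assumed. With drift of 0.2 SD or more against the tested direction and no AZD1775 effect, rejection falls to 0.7% or below. The duration in Section 2.2 ("which is variable in length and lasts up to ~60 hrs in human tumors in-situ") describes S-phase, not marker kinetics, and cannot supply the drift. The number of pairs matters as well: Section 9.2.3.8 reports paired tissue from eight participants for one assay. If only eight pairs were usable here, the 20%, 34% and 65% would become 13%, 19% and 36%.

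Nor do the documents support saying that the biopsies are worthless. The analyses are exploratory, the tests are there to describe change, and Section 9.1 also cites a 50% fall in pCDC2 as an earlier benchmark and adds the ratio to total CDC2. Neither the benchmark nor the ratio removes a time effect on phosphorylation.

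Finally, matching on time would not isolate AZD1775 completely. The second biopsy follows a second cisplatin dose, Section 8.2.1 notes platinum in tissue for up to 180 days, and Section 9.2.3.2 does not require the same lesion twice. That is correct, but it limits the remedy and is no reason to leave an avoidable difference in place.

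**Conclusion.** The concern holds in limited form. Nominal times after cisplatin differ within a pair (5-48 h against about 53-56 h; 29-80 h with the tolerance, 48-80 h if the biopsy must follow the last dose), matching is not required, and no adjustment is planned. The paired change alone therefore cannot separate AZD1775 from the time course after cisplatin.

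The timing follows from the protocol, given 12 h spacing and a simultaneous start. The consequence for error rates is conditional: about 20-65% with 18 pairs only if drift is 0.2-0.5 SD in the tested direction, and lost power if it runs the other way. This affects the reading of exploratory secondary objectives 2 and 4. The primary decision on objective response rate is untouched.

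**What to change.** **Future pairs.** Set the cycle 1 biopsy at the same target hours after cisplatin as the cycle 2 biopsy, which puts it on day 3 of cycle 1, with the same tolerance. This removes the systematic gap. Under two identical 29-80 h windows an individual pair could still differ by up to 80 - 29 = 51 h in either direction, so recorded times are still needed.

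**Wording.** Reconcile Section 1.1 (no tolerance) with Sections 3.1.12, 9.2 and 9.2.3.2, the calendar footnote and Appendix C. Reconcile the day 1 label with the day 2 or 3 label for the first biopsy. State whether the second biopsy may precede the last AZD1775 dose.

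**Pairs already taken.** Keep the all-pairs analysis. Report hours since cisplatin for both biopsies of each pair. Add two sensitivity analyses: the closest-matched pairs, and the change adjusted for the difference in hours. Do not attribute the paired change to AZD1775 alone without them. A subset with the first biopsy on day 3 should not become the main analysis: that would be a post hoc choice, could leave few pairs, and a first biopsy at the 48 h limit is still 5 h short of the nominal 53 h.

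**Cost.** Less flexibility in scheduling the first biopsy, perhaps a few lost pairs, and an imprecise adjustment when pairs are few. The analyses need no new data, because Section 3.1.12 already requires exact biopsy times.
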